4.3 Potential Benefits

Smoking remains the leading preventable cause of early mortality in the US. The proposed research is a clinical trial that will evaluate FDA-approved medications for smoking cessation, customized to individual smokers' nicotine metabolism. Prior research has demonstrated that such an approach can significantly increase abstinence rates. Therefore, the potential benefits of the proposed research include a greater likelihood of smoking cessation and the corresponding health benefits, including longer life expectancy. In addition, this research may benefit others by reducing exposure to secondhand smoke and more generally by contributing to the knowledge base on smoking cessation best practices.

4.4 Participant Renumeration

Participants can be remunerated up to \$50 for participation in this trial, \$25 for each of the two in-person data collection visits.

5.0 DATA SAFETY MONITORING PLAN (DSMP)

For this study, we will use all established ChristianaCare procedures and infrastructure for data and safety monitoring. A Data Safety Monitoring Board will not be used for this study because it is a single center trial that will use FDA-approved drugs with good safety profiles for on-label use. During the course of the study, safety and data quality monitoring will be performed on an ongoing basis by the PI and research team. Study personnel are responsible for collecting and recording all clinical data using the established operating procedures. This includes ensuring that all source document exist for the data on Case Report Forms, ensuring all fields are completed appropriately, and ensuring that all corrections are done according to Good Clinical Practice. Any inconsistencies or deviations will be documented. The study Key Personnel, which include the study physician ([name]), will review data on an ongoing basis and will document reviews by initialing and dating reports. Study personnel conduct 100% quality assurance on data, comparing all hard copy to electronic files.

Staff training will consist of an explanation of the protocol and review of the Case Report Forms. In addition, the duties of each staff person will be outline and all applicable regulations will be reviewed by the PI. Mock sessions with critical feedback will be conducted by the PI. The PI will oversee recruitment and data collection and management.

Monitoring will be conducted in accordance with the ChristianaCare Institutional Review Board (IRB) procedures (SOP: 402.1) regarding Adverse Events. Study staff will administer a side effects checklist to determine any reporting requirements. Should a report rise to the level of a potential Adverse Event, the decision on the course of action for the participant will be determined by [name] after review of the review. In addition, both personnel and participants will be given the contact information should they need to reach a member of the study between assessments. The research team will clinically follow all participants who are discontinued due to a Serious Adverse Event until it resolves and becomes stable, unless a referral to another physician (e.g., specialist) is clinical indicated or requested by the participant. All Adverse Events and Serious Adverse Events will be documented on a ChristianaCare IRB Adverse

Event Form. This information will, in turn, be reported immediately to all necessary regulatory committees and maintained in a unique databased to be reviewed monthly by the PI.

6.0 USE OF PHI AND STORAGE OF STUDY RECORDS:

Self-report, blood, and medical data will be collected and stored as part of this study. Therefore, to protect participant privacy and confidentiality, several safeguards will be implemented to prevent unauthorized access to study data. A unique identification number will be generated for each participant to be used in the dataset that contains collected data. A separate table, housed in a unique location, will be created for storing participant name, address, and telephone contact information. Using this method, no identifying participant information will be directly linked to medical information or other study data. Data will be stored on an electronic folder dedicated to research with access limited to only authorized research personnel on the study protocol. Paper documentation will be stored in a badge protected office in the locked drawer of the research coordinator's desk. Data cannot be transferred to personal computers or other memory devices. In the very rare event of a breach of confidentiality, all IRB procedures will be followed, affected participants will be notified, and appropriate corrective measures to secure the data will be taken. In addition, participants will be provided with any reasonable assistance to help mitigate the risk. The results of this study will be presented only in a summary and/or deidentified fashion in peer-reviewed publications and research presentations.

Information about study participants will be kept confidential and managed according to the requirements of the Health Insurance Portability and Accountability Act of 1996 (HIPAA). Those regulations require a signed participant authorization informing the participant of the following:

- What protected health information (PHI) will be collected from the participants in the study
- Who will have access to that information and for what purposes
- Who will use or disclose that information
- The rights of the research participant to revoke their authorization for use of their PHI

In the even that a participant revokes authorization to collect or use PHI, the PI, by regulation, retains the ability to use all information collected prior to the revocation of participant authorization.

The following PHI will be collected on study participants:

Document: Statistical Analysis Plan

Document Date: March 5, 2020

Official Study Title: A Pilot Pragmatic RCT of a Hospital-based Precision Pharmacotherapy Smoking Cessation Program

NCT#: NCT04897607

Statistical Analysis Plan

Specific Aim 1: *The proposed trial will be acceptable to underserved smokers as measured by the proportions and demographic characteristics of patients who enroll (H1.1), accept pharmacotherapy (H1.2), and complete follow-up (H1.3).*

Descriptive statistics and 95% confidence intervals will be used to summarize the feasibility metrics, namely the numbers and proportions of patients who: 1) were approached, 2) deemed eligible, 3) enrolled, 4) accepted pharmacotherapy, and 5) completed follow-up. To gain a sense of whether study participants may be considered representative of the larger population of ChristianaCare smokers as measured by race and area-level measures of SES, chi-square tests and Wilcoxon rank tests will be conducted. Race is routinely collected for all admitted patients and will permit a comparison between trial participants and the larger population of ChristianaCare smokers. However, no individual-level measures of SES are routinely collected for admitted patients and therefore will not allow for a comparison between trial participants and the larger population. Therefore, census tract measures of poverty (e.g. employment status, income, and education) based on participant residence will be used as a proxy for individual-level SES. The residential addresses for the larger population of ChristianaCare smokers has been previously geocoded and linked to census tract poverty measures,⁴⁸ which will be used to compare the proportions of participants in this trial who reside in each census tract strata.

Specific Aim 2: *Patients assigned to precision care will more readily accept pharmacotherapy (H2.1), achieve greater treatment matching (H2.2), and demonstrate improved abstinence rates (H2.3).*

Three sets of logistic regression models will be used to compare precision pharmacotherapy vs. standard care for each of the binary effectiveness outcome measures: acceptance of pharmacotherapy, treatment matching, and abstinence. Models will adjust for demographics and other covariates, including age, race/ethnicity, nicotine dependence, and indicators of SES (employment status, income, and education).

Exploratory Aim: *Precision pharmacotherapy will improve patient outcome expectancies related to medication effectiveness and safety/side effects, which will be associated with greater use of pharmacotherapy (H3.1) and abstinence (H3.2). Higher rates of treatment matching in precision care will mitigate the reductions in abstinence rates for low-SES/racial minority smokers compared to standard care (H3.3).*

Mediation analyses. Two sets of logistic regression models will be used to evaluate whether patient outcome expectancies mediate the relationship between treatment assignment (precision vs. standard) and the outcome measures use of pharmacotherapy and abstinence. In the first step for each model, treatment condition will be used to predict the outcome measures, adjusting for the same covariates used above. In the second step, patient outcome expectancies will be used to predict the outcome measures, again adjusting for covariates. If both treatment condition and treatment expectancies are significantly associated with outcome measures, a third step will include both predictors to formally test for partial or complete mediation by assessing whether the inclusion of patient outcome expectancies reduces or eliminates the effect for treatment assignment.

Moderation analyses. A series of logistic regression models will be used to evaluate whether greater treatment matching mitigates (i.e., moderates) the lower rates of abstinence typically seen among low-SES/racial minority patients in usual care. The model will include the predictors of treatment matching (dummy coded as yes/no based on whether the participant used the medication matched to their nicotine metabolism rate: NRT for slower metabolizers, varenicline for faster metabolizers), measures of SES (e.g., years of education), and the product of these predictors. If the product, or interaction term, significantly predicts abstinence, that would provide evidence that treatment matching has differential impacts based on the SES of the participant. Post hoc analyses will be employed to describe the nature of the interaction. A

similar, albeit multilevel approach will be used to test for interaction between area-level variables (e.g., census tract poverty levels, tobacco outlet density) and treatment matching.

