Approximately 100 adult current smokers (≥ 5 cigarettes/day), who are patients at the Helen F. Graham Cancer Center & Research Institute (Christiana Care) lung/thoracic clinic who are ages 18 and older. Exclusion criteria include: 1) use of non-cigarette tobacco products or current TUD treatment, 2) psychiatric or other medical contraindications to receiving TUD medication (assessed by the study physician), 3) no telephone, 4) medical instability, 7) inability to communicate in English, 8) unable to consent due to mental status, 9) estimated life expectancy of < 6 months, 10) pregnancy.

The duration of study participation will be approximately 6 weeks from the first through the final study visit.

3.0 STUDY PROCEDURES:

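### SAP Aim 1 checks representativeness with difference tests alone; with about 100 participants a non-significant result would not support it, and no interval for the participant–population difference is planned

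*SAP*

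**What the plan says.** In the SAP, Specific Aim 1 concerns whether the trial is acceptable to underserved smokers, measured in part by who enrolls. The comparison with the source population is introduced with the words "To gain a sense of whether study participants may be considered representative of the larger population of ChristianaCare smokers", and the method is given as "as measured by race and area-level measures of SES, chi-square tests and Wilcoxon rank tests will be conducted". For race, the SAP says: "Race is routinely collected for all admitted patients and will permit a comparison between trial participants and the larger population of ChristianaCare smokers". For socioeconomic status, census-tract measures stand in for individual data, and the SAP will compare the proportions of participants living in each tract stratum with the previously geocoded population.

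The same paragraph plans interval estimates, but for something else: "Descriptive statistics and 95% confidence intervals will be used to summarize the feasibility metrics". Those metrics are the five counts from approach to completed follow-up. No interval, margin, significance level or power is stated for the comparison with the population, and neither the size nor the racial mix of that population is given.

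The protocol (section 2.0) sets the sample at "Approximately 100 adult current smokers".

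**The concern.** Whether participants resemble the source population is a question about similarity. Chi-square and Wilcoxon rank tests address difference. A small p-value is evidence against representativeness. A large one means only that no difference was detected, which with about 100 people can easily happen when a group is clearly under-enrolled.

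The plan names no other inferential output for this comparison, so a reader of the results would have a p-value but no measure of how large a shortfall the data still allow. That matters because Aim 1 is about reaching underserved smokers, and this is the only inferential comparison in the SAP that sets the enrolled sample against the smokers it was drawn from.

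**Working it through.** The documents state no power or precision figure for this comparison, so there is none to reproduce. The check asks how often the planned race test would miss a shortfall, and how wide an interval would be in its place.

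**Inputs**
- n = 100, from protocol section 2.0, both arms combined.
- Two-sided 0.05: assumed, not stated for these tests.
- Reference share p0: not stated; shown from 15% to 50%.
- Reference population treated as known; size not stated.
- Shortfalls of 10 and 5 percentage points: illustrative, not from the documents.

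**Test for one group against the rest.** With k participants in the group, reject when (k − 100·p0)² / [100·p0·(1 − p0)] > 3.84. The chance of missing a shortfall d is the exact binomial probability, at true share p0 − d, that k falls in the non-rejection range.

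Example at p0 = 40%: the denominator is 100 × 0.4 × 0.6 = 24, and √(3.84 × 24) = 9.6. Any count from 31 to 49 is therefore non-significant. At a true share of 30% the probability of landing in that range is 0.451; at 35% it is 0.826.

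| Reference share | Non-significant counts | Miss 10-point shortfall | Miss 5-point shortfall |
|---|---|---|---|
| 15% | 9–21 | 6% | 68% |
| 20% | 13–27 | 20% | 75% |
| 25% | 17–33 | 33% | 81% |
| 30% | 22–38 | 35% | 79% |
| 40% | 31–49 | 45% | 83% |
| 50% | 41–59 | 46% | 82% |

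**Sensitivity, 10-point shortfall**
- The normal approximation gives misses of 24% at a 20% share, 40% at 30%, 46.5% at 40% and 48% at 50%.
- On the same approximation, a comparator of 1,000 people rather than a known share gives 28%, 44%, 50% and 52%. With 5,000 or more, the figures are within about 1 point of the known-share ones.
- A continuity correction raises the exact miss rate to 54% at 40% to 50%.
- A single test over three or four race categories, with illustrative mixes and p0 of 30% to 40%, misses 50% to 55%.

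**What a non-significant result leaves open.** Take 31 of 100 observed against a 40% reference. The statistic is 9² / 24 = 3.375, below 3.84, so the test is non-significant. The Wilson 95% interval for the share is 22.8% to 40.6%. Subtracting 40 gives a difference between −17.2 and +0.6 points: the same data are compatible with a 17-point shortfall.

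**Precision of an interval instead.** Half-width = 1.96·√[p(1 − p)/100]: 7.8 points at 20%, 9.0 at 30%, 9.6 at 40%, 9.8 at 50%.

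**Wilcoxon comparison.** The documents give no distribution for the tract measures, so its power cannot be computed. The logical point does not depend on it.

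**The case against.** Two stronger readings are tempting, and the documents support neither.

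The first is that the tests would miss a 10-point racial shortfall nearly half the time, stated without condition. The main calculation gives that only at reference shares of about 35% or more. At 20% it gives a miss about one time in five, and at 15% about one in sixteen. The documents do not give the racial mix, so only the range can be stated.

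The second is that the SAP will declare the sample representative when p exceeds 0.05. It contains no such rule. The stated purpose is to gain a sense, in a study titled a pilot, with no go/no-go criterion attached and no use of the result in Aim 2 or the Exploratory Aim. The SAP also intends to set out proportions by census-tract stratum, which are informative whatever the p-value. This part of the objection stands: the risk is a misreading that the plan does not guard against, not one that it prescribes. The informal purpose nevertheless favours estimation over testing.

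It is also fair to object that a formal margin-based call for each category would be too much for a pilot of this size. With an illustrative 10-point margin and no true difference, a Wilson lower limit would exclude the shortfall 87% of the time at a 20% share, 70% at 30%, 62% at 40% and 54% at 50%. Excluding both directions would succeed 53% of the time at 20% and only 8% at 50%. A margin should therefore not be required as a decision rule.

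**Conclusion.** The concern holds in a limited form. The planned tests can contradict representativeness but cannot support it, and no interval estimate of the participant–population difference is planned. For race, a true 10-point shortfall would go undetected about 20% of the time at a 20% reference share, about 35% at 30%, and about 45% at 40% to 50%; a 5-point shortfall would be missed about 75% to 83% of the time. These figures rest on a two-sided 0.05 test, 100 participants, a single group against the rest, and a reference share that is known but assumed here. The logical point needs none of these assumptions and covers the tract measures as well. The treatment comparisons are unaffected.

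**What to change.** In SAP Specific Aim 1:

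- Make the main output of this comparison the participant share minus the reference share, with its 95% confidence interval, for each race category and census-tract stratum. For continuous tract measures, report a standardised difference with its interval.
- Keep the chi-square and Wilcoxon p-values as secondary at most, and say that non-significance will not be read as representativeness.
- State the expected half-width with 100 participants: about 8 points at a 20% share, rising to about 10 points at 50%.
- Optionally, name in advance a shortfall that would matter, for the sponsor to choose, as an aid to reading the intervals and not as a formal rule for each category.

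This uses the same data and changes only the SAP text. The downside is that the pilot will often have to report that it is not precise enough to tell.

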3.1 Overview of Proposed Research Design

This investigation employs a randomized controlled trial (RCT) study design. Participants will be randomized into either precision pharmacotherapy, where they will receive a personally-tailored recommendation for a TUD medication based on their NMR plus standard care, or to standard care only. Standard care will adhere to the Ask-Advise-Connect model where participants are asked about tobacco use, advised to quit smoking, offered a choice of FDA-approved TUD medication and offered a referral to the Delaware Quitline for access to counseling services and medications.

Upon enrollment into the study, the research assistant will verify demographic data, administer a baseline survey, and coordinate testing for the NMR at their in-person intake visit. Patients will be randomized to the precision or standard care arms in a 1:1 ratio. Following receipt of the NMR test results and randomization, the research assistant will follow-up with a pre-quit telephonic visit to review procedures with participants. For standard care, the research assistant will provide information on FDA-approved TUD medications and offer to coordinate the process of starting on a medication of the participants' choice (i.e., nicotine patch or varenicline), which participants can decline. Participants randomized to precision pharmacotherapy will be provided with their NMR result, information on how NMR impacts TUD treatment, and a personalized recommendation for medication based on their NMR result (i.e., varenicline for faster metabolizers, nicotine patch for slower metabolizers). Similar to standard care procedures, participants will be offered either the nicotine patch or varenicline and will not be required to choose the medication based on their personalized recommendation, or any medication. For participants in both conditions who opt for medication, per participant preference, medications can be prescribed by the study physician ([name]) or the patient can be referred to the Delaware Quitline for no-cost medications, a free service available to all Delaware residents. A 1-week follow-up telephonic visit will be conducted to collect data related to medication use, quit date or smoking rate, and side-effects. Finally, a 1-month follow-up in-person visit will be arranged to complete a follow-up survey and to assess smoking status.

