3.3 Study Procedures & Data Collection

The following study procedures will be implemented. A description of the measures used to collect data during these procedures is provided below.

- **Intake Session (completed during clinic visit)**
 - Participants will complete a self-report survey of demographics, smoking history, and beliefs about the use of smoking cessation aids.
 - **[Women only]** A pregnancy screen will be administered for women capable of becoming pregnant (55 and under). NOTE: For safety reasons, pregnant women will not be eligible to participate in the research study.
 - The research assistant will complete the blood draw to be used for a nicotine metabolite ratio (NMR) test and arrange for the sample to be transported to the laboratory for processing.
- **Randomization:** Following completion of the 'intake session' and receipt of NMR testing results, participants will be randomized in a 1:1 ratio to either of the following conditions:
 - **Treatment Plan Option 1 (Standard Care):** Standard smoking cessation counseling will be offered + participant choice of nicotine patches or varenicline. Participants are also free to decline either medication.
 - **Treatment Plan Option 2 (Precision Pharmacotherapy):** Standard smoking cessation counseling will be offered + a recommendation to take either the nicotine patch or varenicline based on the results of the NMR test. Regardless of the recommendation, it would still remain the participant's choice to be prescribed either nicotine patches or varenicline. Participants are also free to decline either medication.
- **Pre-Quit Telephonic Visit:** This visit will take place after the NMR results have been received and randomization is complete, approximately 7-14 days following the intake session (depending on lab processing time).

- Participants will be informed of their treatment condition, including the recommended medication if assigned to 'treatment plan option 2' (i.e., the precision pharmacotherapy arm).
- Participants will be offered their choice of either the nicotine patch or varenicline. Participants will be reminded that taking medication is not a condition of participation in the study. In addition, participants assigned to 'treatment plan option 2' (i.e., the precision pharmacotherapy arm) will not be required to accept only the medication recommended to them based on the results of NMR testing.

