- For participants who elect to take a medication, the research assistant will communicate with the study physician ([name]), or the investigators at the Center for Advanced GYN & Minimally Invasive ([name] or [name]) to arrange for a prescription and/or referral to the Delaware Quitline, per participant preference.
- Even for participants who receive a prescription in the clinic or at the Center for Advanced GYN & Minimally Invasive Surgery, a referral to speak with a smoking cessation counselor, which is made available at no-cost to all Delaware residents through the Delaware Quitline.
- Follow-up Telephonic Visit:** This session will occur one week after the pre-quit telephonic/virtual visit.
 - Participants will answer brief questions regarding medication use, quit date or smoking rate if still smoking, and side effects.
- In-Person Assessment:** This session will occur four weeks after the pre-quit telephonic/virtual visit. The research assistant will arrange to meet participants at the clinic.
 - Participants will again complete a brief assessment of medication use, quit date or smoking rate if still smoking, and side effects.
 - Participants who self-report smoking cessation will complete a carbon monoxide (CO) reading by breathing into a machine provide a biochemical confirmation of smoking status.

The measures referenced above will be administered accordingly:

Study Measure	Intake Session Enrollment (in-person)	Pre-Quit Visit Week 0 (phone)	Follow-Up Visit Week 1 (phone)	Final Assessment Week 4 (in-person)
Demographics	X			
Smoking History	X			
NMR	X			
Medication use, quit date or smoking rate, side-effects			X	X
Carbon Monoxide reading				X

- **Demographics.** The research assistant will confirm demographic data collected from the EHR and collect additional characteristics, including address, phone number, date of birth, race/ethnicity, employment status, education level, and income.
- **Smoking history.** Participants will be asked standard questions about cigarette use, including the number of cigarettes smoked per day, the age of smoking onset, whether the participant ever quit smoking previously and for how long, and whether the participant ever utilized smoking cessation aids previously. In addition, participants will be administered the first item from the Fagerström Test for Nicotine Dependence (FTND), a measure of nicotine tolerance and withdrawal.¹⁷

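### Aim 2 models: with at least 7 slopes on about 100 participants, unpenalised logistic regression modestly overstates a real arm effect on abstinence, and NMR group is not a named covariate in the matching model

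*SAP*

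**What the plan says.** SAP, Specific Aim 2: "Three sets of logistic regression models will be used to compare precision pharmacotherapy vs. standard care" on acceptance of pharmacotherapy, treatment matching and abstinence. On adjustment: "Models will adjust for demographics and other covariates, including age, race/ethnicity, nicotine dependence, and indicators of SES (employment status, income, and education". The list is open-ended. The SAP does not say how the covariates are coded, and it names no penalised, exact or other small-sample method, so maximum likelihood (ML) is the default reading. It gives no expected abstinence rate or event count.

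Protocol 2.0 plans "Approximately 100 adult current smokers". Protocol 3.3 collects "race/ethnicity, employment status, education level, and income" among the demographics, without response categories. The SAP's Moderation analyses paragraph offers years of schooling as an example SES measure, which would be a single slope.

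On NMR, Protocol 3.1 gives the precision arm a "personalized recommendation for medication based on their NMR result". Protocol 3.3 places randomisation after the test: following "receipt of NMR testing results, participants will be randomized in a 1:1 ratio". The SAP's Moderation analyses paragraph defines matching by whether the participant "used the medication matched to their nicotine metabolism rate". NMR group is not among the covariates named for Aim 2, and no stratification by it is described.

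**The concern.** ML logistic regression is biased away from zero when there are few events per estimated slope. Abstinence (H2.3) is likely to be the sparsest of the three outcomes, and the adjustment set is sizeable for 100 participants. If precision care works, the reported OR will on average look better than the truth. That matters most if a pilot OR is later used to size a larger trial, although the SAP does not state that use.

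The second part concerns H2.2. Matching is built from NMR group, and the group is fixed before allocation. If standard-care participants choose the matched drug more often in one NMR group than in the other, a chance imbalance in NMR between arms adds noise that a covariate already in hand would remove.

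**Working it through.** The plan states no power, event count or effect size, so there is no figure of its own to reproduce.

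**Inputs from the documents.** About 100 participants at 1:1, so 50 per arm. Slopes: arm (1) + age, race/ethnicity, dependence, employment, income and education (6) = 7 at one term each. The only anchor for abstinence is the protocol's background remark that quit rates in hospital programmes seldom pass 25%.

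**Assumptions.** Overall abstinence of 15%, 25% or 32%, giving 15, 25 or 32 events (32 lies above the anchor). True OR 1 or 2 (log-OR 0.693). Modest covariate effects (log-OR 0.15 to 0.3). Race/ethnicity in 4 groups, employment in 3, income and education in 4 each. Dummy-coding all four of these gives 14 slopes: arm 1 + age 1 + dependence 1 + 3 + 2 + 3 + 3.

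**Events per slope** = events / slopes. With 7: 15/7 = 2.1, 25/7 = 3.6, 32/7 = 4.6. With 14: 1.1, 1.8, 2.3.

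**Abstinence, true OR 2, 2000 simulated trials per row** (percentages from unrounded means; ML rows leave out fits in which the arm itself separated):

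| Slopes | Events | ML mean log-OR | ML RMSE | Firth mean | Firth RMSE |
|---|---|---|---|---|---|
| 7 | 15 | 0.82 (+19%) | 0.75 | 0.71 | 0.63 |
| 7 | 25 | 0.78 (+13%) | 0.58 | 0.70 | 0.50 |
| 7 | 32 | 0.76 (+10%) | 0.53 | 0.69 | 0.47 |
| 14 | 15 | 0.95 (+37%) | 1.00 | 0.71 | 0.69 |
| 14 | 25 | 0.86 (+25%) | 0.68 | 0.70 | 0.53 |
| 14 | 32 | 0.84 (+21%) | 0.63 | 0.69 | 0.50 |

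At 25 events the mean ML estimate corresponds to an OR of exp(0.78) = 2.2 with 7 slopes and exp(0.86) = 2.4 with 14. Repeat 7-slope simulations gave ML means of 0.80 to 0.84, 0.76 to 0.79 and 0.76 to 0.78 at 15, 25 and 32 events.

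- *Bias beside total error, 7 slopes.* (bias/RMSE)²: (0.13/0.75)² = 3.0%, (0.09/0.58)² = 2.4%, (0.07/0.53)² = 1.7% of mean squared error. Firth lowers RMSE by 1 − 0.63/0.75 = 16%, 1 − 0.50/0.58 = 14% and 1 − 0.47/0.53 = 11%. Most of that is lower variance from shrinkage.
- *At OR 1, 7 slopes.* The mean ML log-OR was within 0.012 of zero. Null rejection was 4.1% to 5.8%. Coverage of the ML interval at OR 2 was 94% to 96%. The Monte Carlo standard error of a 5% rate is √(0.05 × 0.95/2000) = 0.5 points.
- *With 14 slopes.* ML null rejection was 6.0% / 6.6% / 6.9%. Some coefficient separated in 77% / 48% / 32% of trials, but the arm did so in only 0.9% / 0% / 0%.
- *Power at OR 2.* 7 slopes: ML Wald 20% / 31% / 35%, Firth profile 20% / 29% / 33%. 14 slopes: 22% / 31% / 35% against 18% / 27% / 31%.

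**Matching.** Assumed slow-metaboliser share 30% or 50%; 24 to 39 matching events; 4000 simulated trials per scenario; ML with the 7 slopes against 8 (NMR added).

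- *Standard-care matching differs by NMR group* (45%/15% or 50%/10% slow/fast): variance of the standardised risk difference falls 4% to 10%, and power rises 2 to 5 points (for example 59% to 64%).
- *It does not differ* (30%/30%): variance rises 1% to 2%; power stays at 34% to 35%.
- *Null rejection:* 5.5% to 6.0% with NMR, 5.1% to 5.8% without.
- *Log-OR scale:* in a simpler scenario (50% fast; slow/fast matching 40%/20% under standard care and 60%/40% under precision; other covariates left out), adding NMR moved the mean arm log-OR from 0.885 to 0.936 and its SE from 0.425 to 0.442. The ratio goes from 0.885/0.425 = 2.08 to 0.936/0.442 = 2.12.
- *Sparsity applies here too:* 24/8 = 3.0 to 39/8 = 4.9 events per slope. ML with 8 slopes overstated the conditional arm log-OR by 8% to 15%, against 7% to 11% with 7.

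**The case against.** The case for leaving the plan alone is substantial. With 7 slopes the bias is 2% to 3% of mean squared error, the test and interval behave, and imprecision from 100 participants dominates. Firth gives up a little power in a pilot that has little. The worst figures come from the 14-slope coding, whose category counts are assumed; the one coding hint in the SAP points to a single slope for education. The covariate list is open, so NMR group is not excluded. Adding it raises the SE of the log-OR and makes the OR conditional on NMR group.

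All of that stands, and it limits the point without removing it. The 7-slope bias appears in every non-null scenario tried, and Firth removes it while lowering total error. The NMR gain shows in power and in the risk difference, not in the SE of the log-OR, so the risk difference has to be reported for that gain to be visible. Adding NMR to a plain ML fit would slightly enlarge the small-sample bias, so the matching model needs the same penalised fit as abstinence.

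Four stronger readings are tempting and are not supported:
- *That the H2.3 test is invalid or prone to false positives.* With 7 slopes, null rejection is nominal and there is no bias at OR 1. The slight excess arises only under the assumed dummy coding.
- *That separation will wreck the arm estimate.* Where separation occurs, it is almost always in a nuisance dummy.
- *That covariates should be dropped.* Firth copes with the full set.
- *That leaving out NMR biases H2.2.* Under randomisation it does not; it can only cost precision.

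**Conclusion.** The point holds as a modest, inexpensive improvement; it is not an error that invalidates Aim 2. If the true OR is 2 and there are 15 to 32 abstinence events, the default ML fit overstates the arm log-OR by about 10% to 19% with 7 slopes, and by more if the factors are dummy-coded. The event counts, effect size, covariate distributions and coding are assumptions, because the documents supply none of them; at the background anchor of about 25 events the figure is about 13%. Naming NMR group in the matching model is worth 2 to 5 points of power if standard-care matching differs by NMR group, and close to nothing otherwise. Those gains were computed with ML fits; the power of the Firth matching model was not simulated.

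**What to change.** Amend SAP Specific Aim 2 as follows, keeping every named covariate.

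1. Fit the abstinence and treatment-matching models by Firth penalised likelihood, with a penalised profile-likelihood test and 95% CI for the arm OR. Do the same for acceptance if either outcome category is sparse. The profile version matters: Wald tests after Firth were conservative in simulation (3.4% to 4.3% null rejection with 7 slopes).
2. State the coding of each covariate.
3. Report absolute rates from raw counts, because Firth fitted probabilities are pulled towards 50%.
4. Add NMR group (slower/faster, as classified for the recommendation) to the matching model. Report the standardised risk difference beside the OR, and note that the OR is then conditional on NMR group. Say how the fitted probabilities behind the risk difference are obtained, given the pull in item 3; re-estimating the intercept so that fitted and observed totals agree is one way.

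Cost: SAP wording only, with no new data. For abstinence, Firth costs up to about 2 points of power with 7 slopes and about 4 with 14, part of the latter reflecting the raised ML null rejection. NMR adds 1% to 2% to the variance if matching does not differ by NMR group.
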